** Cisplatin or carboplatin and etoposide (CE) will be administered with standard of care pre-medications and pre/post hydration every 3 weeks.

*** A maximum of 4 cycles of platinum and etoposide will be given.

Rev. Add1

**** After 4 cycles of combination therapy in the investigational arm (Arm A), nivolumab only will be continued as maintenance therapy, **administered at 240 mg IV over 30 minutes every 2 weeks** until progressive disease, unacceptable toxicity, patient desire to discontinue study therapy or up to 2 years (or 50 doses) maximum.

Arm B Description (Standard arm) – Cycles 1-4***					
Agent	Pre-medications**; Precautions	Dose	Route	Schedule	Cycle Length
Carboplatin*	Dexamethasone 5-HT3 antagonist Aprepitant or Fosaprepitant	AUC 5 or 6 IV over 30 to 60 minutes	IV	Day 1	21 days (3 weeks)
Cisplatin*	Dexamethasone 5-HT3 antagonist Aprepitant or Fosaprepitant	75mg/m2 IV over 60 to 120 minutes		Day 1	
Etoposide	Dexamethasone 5-HT3 antagonist	100 mg/m2 IV over 60 to 120 minutes		Days 1, 2, 3 after platinum infusion is completed	

Carboplatin/Cisplatin is given first, followed by etoposide.

- * The decision to administer cisplatin or carboplatin is at the discretion of the treating physician. If the choice is made to administer carboplatin, starting dose of AUC 5 or 6 is at the discretion of the treating physician.
- ** Cisplatin or carboplatin and etoposide (CE) will be administered with standard of care pre-medications and pre/post hydration every 3 weeks.
- *** A maximum of 4 cycles of platinum and etoposide will be given then the patient will proceed to observation until disease progression or non-protocol treatment regimen is initiated.

Rev. Add3

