5.4.1 Cisplatin/Carboplatin and Etoposide Supportive Care

NOTE: Dose reductions for all events are permanent and should be for all subsequent cycles. Patients may receive a maximum of two chemotherapy dose reductions. If a third chemotherapy dose reduction is required, the patient should discontinue chemotherapy protocol treatment. If different percentages of dose reductions for a specific drug are required because of two different types of toxicities, the greater percentage dose reduction should be undertaken.

Rev. Add3

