5.4.1.1 Hematologic Toxicity

Neutropenia and/or Thrombocytopenia

Granulocyte or platelet counts for Day 1: Based on counts within 3 days of the start of each cycle, give the following:

Granulocytes/mm ³		Platelets / mm ³	Cisplatin/carboplatin and etoposide
ANC ≥ 1,500	and	PLT ≥ 100,000	100%
ANC < 1,500	and/or	PLT < 100,000	Hold dose*

* Hold cisplatin/carboplatin and etoposide; repeat counts at least once weekly and reinstitute therapy at 100% when granulocytes ≥ 1,500/mm³ and platelets ≥ 100,000/mm³ if recovery within 7 days.

If cisplatin administered, reinstitute at 75% of the original dose if more than 7 days. If carboplatin administered, reinstitute carboplatin AUC with decrease by one dose level (i.e. starting dose of AUC 6 dose reduction 1= AUC 5), if more than 7 days.

If counts do not reach these levels within 3 weeks of the next scheduled treatment, discontinue chemotherapy protocol therapy.

Neutropenia or Febrile Neutropenia

For nadir neutropenia in the absence of fever or with fever that is successfully treated by oral antibiotics, there will be no dose adjustment. Filgrastim, sargramostim, or pegfilgrastim are allowed (for the next cycle of chemotherapy). Growth factors may be used in

accordance with American Society of Clinical Oncology (ASCO) and NCCN guidelines.

For treatment delays (hold both chemotherapy and nivolumab) due to chemotherapy toxicities of more than 7 days, both chemotherapy drugs, cisplatin and etoposide, should be dose reduced by 25%. If carboplatin administered, reinstitute carboplatin AUC with decrease by one dose level (i.e. starting dose of AUC 6 dose reduction 1= AUC 5), if more than 7 days.

Rev. Add4

For neutropenic fever (ANC <1000/mm³ with a single temperature of >38.3 degrees C (101 degrees F) or a sustained temperature of ≥ 38 degrees C (100.4 degrees F) for more than one hour) requiring intravenous antibiotics, the doses of all chemotherapy drugs should be reduced by 25% for the next cycle. If carboplatin administered, reinstitute carboplatin AUC with decrease by one dose level (i.e. starting dose of AUC 6 dose reduction 1= AUC 5), if more than 7 days. If counts do not recover within 3 weeks, discontinue chemotherapy protocol therapy.

Thrombocytopenia

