For grade 4 nadir platelet count decrease (platelets < 25,000 mm³), the dose of all chemotherapy drugs should be reduced by 25% from the previous dose for the next cycle. If carboplatin administered, reinstitute carboplatin AUC with decrease by one dose level (i.e. starting dose of AUC 6 dose reduction 1= AUC 5), if more than 7 days. If counts do not recover within 3 weeks, discontinue chemotherapy protocol therapy.

Anemia

No dose reductions will be made for anemia. Patients should be supported per the treating physician's discretion. The use of blood transfusions for anemia will be allowed as indicated. The use of growth factors for anemia is not permitted during cycle 1 for patients and may be used for cycle 2 (please refer to supportive care guidelines in Section [5.5](#)).

5.4.1.2

Gastrointestinal Toxicity, Nausea and Vomiting

All patients should receive antiemetics* to prevent nausea and vomiting. Specific antiemetic therapy is left to the discretion of the treating physician (steroids and 5-HT3 antagonists should be used). If vomiting is severe, consider hospital admission and/or use of aprepitant if possible. Do not modify chemotherapy doses, until antiemetics have been maximally optimized.

*Aprepitant, when given once daily for 14 days as a 100 mg capsule with an oral contraceptive containing 35 mcg

of ethinyl estradiol and 1 mg of norethindrone, decreased the AUC of ethinyl estradiol by 43% and decreased the AUC of norethindrone by 8%. Women of childbearing potential using pregnancy contraception that includes ethinyl estradiol should not receive Aprepitant for the treatment of nausea/delayed emesis. Patients may change to a different method of contraception if they wish to use Aprepitant.

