5.4.1.4 Nephrotoxicity (based on measured or calculated creatinine clearance)

Creatinine Clearance (ml/min)	Cisplatin*
≥ 60	100%
$59 - 50$	67%
< 50	0**

* Please note that the % dose administered is based on the original starting dose of cisplatin (75mg/m²).

**Only patients randomized to Arm A will receive Nivolumab. If serum creatinine clearance is < 50 ml/min on day 1 of the next cycle, delay the start of that cycle for up to 2 weeks (check creatinine at least weekly). If CrCl decrease persists beyond 2 weeks, skip cisplatin for that cycle and proceed with etoposide and nivolumab. NOTE: The etoposide and nivolumab doses will be held if cisplatin is held until a decision is made to skip cisplatin for the current cycle so that all drugs are kept on the same schedule. If the serum creatinine returns to \geq 50 ml/min within 3 weeks of original hold, cisplatin may be reinstated at 67% of the full dose during the next cycle (permanent dose reduction). A more aggressive hydration regimen (as tolerated by patient clinical state) should be instituted as well with all subsequent doses of cisplatin. If CrCl does not recover to \geq 50 ml/min after 3 weeks, remove patient from all protocol therapy.

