5.4.1.9 Grade 3 or 4 Non-Hematologic Toxicity

If patient develops grade 3 or 4 non-hematologic toxicity attributed to protocol therapy but not detailed above [excluding the following: anorexia, fatigue and fever without grade 3 or 4 neutrophil count decrease (neutropenia)] hold all therapy. Therapy can be restarted if the toxicity has resolved to < grade 1 by the time of the next treatment. Doses of all chemotherapy should then be reduced by 25% (of the dose received during the previous cycle). If carboplatin administered, reinstitute carboplatin AUC with decrease by one dose level (i.e. starting dose of AUC 6 dose reduction 1= AUC 5). If chemotherapy is held for more than 3 weeks, remove the patient from all protocol therapy.

A clinically relevant overlap in toxicity may arise between the immune-related dermatologic and cardiac toxicities attributed to nivolumab and dermatologic and cardiac toxicities attributed to etoposide. The management of overlapping toxicities should be guided by clinical judgment and an assessment of the most likely causative etiology, with special consideration given to the potential

for immune-mediated toxicities. Nivolumab administration should be delayed for toxicities as indicated in the management algorithms ([Appendix III](#)) that in the opinion of the treating physician are related to nivolumab. Please refer to Section [5.4.2.2](#).

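### Section 5.4.1 takes cisplatin reductions from the original dose in some rules and the previous dose in others, so two 25% reductions can give 42.19 or 56.25 mg/m2 depending on which toxicity came first

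*Combined protocol and SAP*

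**What the plan says.** Both arms give cisplatin, where chosen, at "75mg/m2 IV over 60 to 120 minutes" (Section 5.1), and "A maximum of 4 cycles of platinum and etoposide will be given". Section 5.4.1 makes every dose reduction permanent, allows two, and stops chemotherapy if a third is required. Where two types of toxicity call for different percentages for one drug, "the greater percentage dose reduction should be undertaken".

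The subsections then set the individual reductions:

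- **Original dose.** For cisplatin after a day-1 count hold (5.4.1.1 footnote), "reinstitute at 75% of the original dose if more than 7 days". The renal table (5.4.1.4) says: "Please note that the % dose administered is based on the original starting dose of cisplatin". The neurotoxicity table (5.4.1.6) carries the same note, gives 75% for grade 2, and adds a 50% step if grade 2 recurs at 75%. The bilirubin table for etoposide (5.4.1.3) also uses the starting dose.
- **Previous dose.** For grade 4 nadir platelets (5.4.1.1), "the dose of all chemotherapy drugs should be reduced by 25% from the previous dose for the next cycle". For other grade 3 or 4 non-hematologic toxicity (5.4.1.9), "Doses of all chemotherapy should then be reduced by 25% (of the dose received during the previous cycle").
- **No reference dose named.** For treatment delays of more than 7 days (5.4.1.1), "both chemotherapy drugs, cisplatin and etoposide, should be dose reduced by 25" per cent. The neutropenic-fever rule in the same subsection also asks for 25% without naming a base.

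**The concern.** A first 25% reduction is the same under either base. A second is not. A rule based on the original dose ignores any reduction already made, while a rule based on the previous dose compounds it. Mixing the two makes the result depend on the order of the toxicities. It also lets a second event under an original-dose rule return the dose the patient already receives.

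Sites in both arms must act on these rules. Two sites following the text faithfully could give different cisplatin doses to patients with the same toxicities, or disagree on whether the limit of two reductions has been reached and chemotherapy must stop. What is at stake is patient safety and uniform delivery of the chemotherapy common to both arms.

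**Working it through.** The plan states no dose after two reductions, so there is no figure of its own to reproduce. The check applies the written rules in sequence.

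**Inputs.** Starting cisplatin dose S = 75 mg/m2 and at most 4 cycles (Section 5.1); reductions permanent, at most two (5.4.1); percentages and bases as listed above.

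**Formulas.** Let d be the current dose.

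- Original-dose rule (count hold of more than 7 days; first grade 2 neurotoxicity): new dose = 0.75 × S.
- Previous-dose rule (grade 4 platelets; other grade 3 or 4 non-hematologic toxicity): new dose = 0.75 × d.

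**First reduction.** 0.75 × 75 = 56.25 mg/m2 under either formula.

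**Two different toxicities, each calling for 25%.**

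| First event | Second event | Dose after first | Dose after second |
|---|---|---|---|
| Count hold >7 days | Grade 4 platelets | 56.25 | 0.75 × 56.25 = 42.19 |
| Grade 4 platelets | Count hold >7 days (footnote) | 56.25 | 0.75 × 75 = 56.25 |
| Grade 2 neurotoxicity | Grade 4 platelets | 56.25 | 42.19 |
| Grade 4 platelets | Grade 2 neurotoxicity (first episode) | 56.25 | 56.25 |

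Replacing grade 4 platelets with another grade 3 or 4 non-hematologic toxicity under 5.4.1.9 gives the same figures.

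**Size of the gap.** 56.25 − 42.19 = 14.06 mg/m2. That is 14.06/56.25 = 25% of the higher dose, or 14.06/75 = 18.75 percentage points of the starting dose.

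**Do the general rules in 5.4.1 remove it?**

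- Permanence: no. No dose rises in any row.
- Maximum of two: no. Each row has at most two reductions and fits within 4 cycles.
- Tie-break: no. It applies when the percentages differ, and here both are 25%.

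**Second count hold of more than 7 days.** By the footnote: 0.75 × 75 = 56.25 mg/m2, no further reduction. By the delay paragraph, if its 25% is taken from the current dose: 0.75 × 56.25 = 42.19 mg/m2. Both are in 5.4.1.1 and both cover the event. Reading the delay paragraph as compounding would also make the count-hold/platelet pair 42.19 in either order, but only by overriding the footnote. The neurotoxicity/platelet pair would still depend on order.

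**Effect on the limit of two.** Take two count holds of more than 7 days with the dose left at 56.25, then grade 4 platelets. If the second hold counts, the platelet event is a third reduction and chemotherapy stops. If it does not, the platelet event is the second reduction and the dose is 42.19 mg/m2. Section 5.4.1 does not say which.

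**Would one base throughout be enough?** All from the previous dose gives 42.19 in either order and on a repeat. All from the original dose gives 56.25 in either order, but a repeat brings no further reduction unless a second step is written in, as 5.4.1.6 does. These figures show the size of the conflict only; they do not favour either base.

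**The case against.** **Different bases need not be an error.** The renal and bilirubin tables map current organ function to a fraction of full dose, while the platelet rule and 5.4.1.9 respond to an event. Each states its base, so a site applying one rule alone knows what to do. That is fair, and a single base is not required. The difficulty arises when rules meet in one patient, which the text does not address for equal percentages.

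**The tie-break may settle some pairs.** A reader might cite creatinine clearance of 50–59 mL/min (67% of original) with grade 4 platelets. Applied literally, renal first gives 75 × 0.67 = 50.25, then 50.25 × 0.75 = 37.69 mg/m2; platelets first gives 56.25, then 50.25 mg/m2. But the percentages there are 33% and 25%, so the greater-percentage rule may apply and give 50.25 in either order. Whether it covers sequential as well as simultaneous toxicities is unclear, but this pair is not a demonstrated conflict.

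**Repeat toxicity usually does bring a further reduction.** A reader might infer a general failure to reduce on repeat. The documents do not support that. Recurrent grade 2 neurotoxicity has a written 50% step, and repeat events under the platelet rule and 5.4.1.9 compound. Only a second count hold of more than 7 days on cisplatin is affected.

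**A restart at an unchanged dose is not a reduction.** That is a natural reading of the limit, but the text does not state it, and the decision to stop chemotherapy turns on it.

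**The reach is limited.** Carboplatin, an equal option at physician discretion, steps down by AUC level and is outside these figures. With 4 cycles, a second sequential reduction can affect only cycles 3 and 4. Section 5.4 describes these rules as guidelines alongside the prescribing information. All of this stands and limits the weight of the point.

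**Conclusion.** The conflict is real but narrow. On the written rules, two 25% cisplatin reductions, one from the original dose and one from the previous dose, end at 42.19 or 56.25 mg/m2 according to order, and nothing in 5.4.1 resolves it. Separately, 5.4.1.1 gives two supportable doses for a second count hold of more than 7 days, and 5.4.1 leaves unclear whether an unchanged dose uses up one of the two permitted reductions.

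This assumes the cisplatin start of 75 mg/m2, a literal reading of each rule, and the footnote reading for count holds in the order comparison.

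A reader might go further and infer an effect on PFS, on the comparison of toxicity rates, or a bias between arms. The documents do not support that. The chemotherapy rules are the same in both arms, no frequency of patients with two reductions is given, and the sample size and power in Section 9.4 are not touched. The case for correction rests on patient safety and consistent treatment delivery.

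**What to change.** The sponsor should reconcile 5.4.1, 5.4.1.1, 5.4.1.3, 5.4.1.4, 5.4.1.6 and 5.4.1.9 by stating in 5.4.1:

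1. which reference dose each percentage uses, including the treatment-delay and neutropenic-fever rules that now name none;
2. how successive reductions combine, including whether the greater-percentage rule covers sequential as well as simultaneous toxicities and what happens when the percentages are equal;
3. what happens on a repeat count hold of more than 7 days, so that the footnote and the delay paragraph agree;
4. what counts toward the maximum of two reductions, in particular an event that leaves the dose unchanged.

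The subsections should then be aligned with that statement. The sponsor chooses the rule; no base or dose is proposed here. The cost is protocol wording only, with no added patients or procedures.

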5.4.1.3 Hepatic toxicity

This table only lists Etoposide dose modifications.

Bilirubin	Etoposide*
$\leq 1.5 \times \text{ULN}$	100%
$> 1.5 - 3.0 \times \text{ULN}$	50%
$> 3.0 \times \text{ULN} - \leq 5.0 \times \text{ULN}$	30%
$> 5 \times \text{ULN}$	Hold**

* Please note that the % dose administered is based on the original starting dose of etoposide (100mg/m²).

** For bilirubin greater than 5 X ULN it is recommended not to use etoposide for that cycle but this is at the discretion of the treating physician. If holding, repeat labs on a weekly basis for up to 3 weeks until total bilirubin is $\leq 5 \times \text{ULN}$. The cisplatin and nivolumab doses should also be held if etoposide is held so that all drugs are kept on the same schedule. If bilirubin improves within 3 weeks to $\leq 5 \times \text{ULN}$, then resume treatment and use reduced dose per table above. If bilirubin does not improve to $\leq 5 \times \text{ULN}$ within 3 weeks, discontinue all protocol therapy.

A clinically relevant overlap in toxicity may arise between the immune-related hepatic toxicity attributed to nivolumab and hepatic toxicity attributed to etoposide. The management of hepatic toxicity should be guided by clinical judgment and an assessment of the most likely causative etiology, with special consideration given to the potential for immune-mediated hepatic toxicity. Nivolumab administration should be delayed for toxicities as indicated in the management algorithms ([Appendix III](#)) that in the opinion of the treating physician are related to nivolumab. Please refer to Section [5.4.2.2](#).

5.4.1.4 Nephrotoxicity (based on measured or calculated creatinine clearance)

Creatinine Clearance (ml/min)	Cisplatin*
≥ 60	100%
$59 - 50$	67%
< 50	0**

* Please note that the % dose administered is based on the original starting dose of cisplatin (75mg/m²).

**Only patients randomized to Arm A will receive Nivolumab. If serum creatinine clearance is < 50 ml/min on day 1 of the next cycle, delay the start of that cycle for up to 2 weeks (check creatinine at least weekly). If CrCl decrease persists beyond 2 weeks, skip cisplatin for that cycle and proceed with etoposide and nivolumab. NOTE: The etoposide and nivolumab doses will be held if cisplatin is held until a decision is made to skip cisplatin for the current cycle so that all drugs are kept on the same schedule. If the serum creatinine returns to \geq 50 ml/min within 3 weeks of original hold, cisplatin may be reinstated at 67% of the full dose during the next cycle (permanent dose reduction). A more aggressive hydration regimen (as tolerated by patient clinical state) should be instituted as well with all subsequent doses of cisplatin. If CrCl does not recover to \geq 50 ml/min after 3 weeks, remove patient from all protocol therapy.

5.4.1.5 Hypomagnesemia

Hypomagnesemia is not an indication for stopping therapy. Oral or parenteral magnesium supplementation is indicated for serum magnesium levels < 1.5 mEq/L.

5.4.1.6 Nervous System Disorder (Neurologic Toxicity)

Grade	Cisplatin*
0-1	100%
2	75%**
3	0***

* Please note that the % dose administered is based on the original starting dose of cisplatin (75mg/m²).

** Patients with a grade 2 nervous system disorder (neurotoxicity) should hold all protocol treatment until recovery to grade 1 or less, then administer 75% dose. If grade 2 nervous system disorder (neurotoxicity) recurs with 75%, drug will be given at 50% upon resolution of nervous system disorder (neurotoxicity) to grade 1 or less. If grade 2 nervous system disorder (neurotoxicity) persists for 3 weeks, remove the patient from all protocol therapy.

*** Discontinue all protocol therapy for nervous system disorder (neurotoxicity) \geq grade 3.

5.4.1.7 Allergic Reactions

Discontinue infusion that has led to allergic reaction promptly if \geq grade 3 anaphylaxis develops.

Suggested Management of Allergic Reaction:

In case of mild allergic symptoms (e.g., Grade 1 – systemic intervention not indicated; Grade 2 – oral intervention indicated), symptomatic treatment may be given (e.g., oral antihistamine or topical corticosteroids).

Patient experiencing significant allergic reaction should be managed according to local institutional standards. A combination of corticosteroids, antihistamines, nebulized

respiratory therapy with beta (2) agonists and isotonic fluid support should be employed as appropriate based on patient's clinical condition.

For Grade 3 or Grade 4 symptoms: (Grade 3: bronchospasm; hospitalization indicated for clinical sequelae; intravenous intervention indicated; Grade 4: life-threatening consequences; urgent intervention indicated):

Immediately discontinue infusion that has led to Grade 3 or Grade 4 allergic reaction. Begin an IV infusion of normal saline and treat the subject as follows: Recommend bronchodilators, epinephrine 0.2 to 1 mg of a 1:1,000 solution for subcutaneous administration, 0.3 mg of a 1:1,000 solution for intramuscular administration, or 0.1 to 0.25 mg of a 1:10,000 solution slowly for IV administration, and/or diphenhydramine 50 mg (oral or IV) with methylprednisolone 100 mg IV (or equivalent), as needed. Subject should be monitored until the Investigator is comfortable that the symptoms will not recur. Investigators should follow their institutional guidelines for the treatment of anaphylaxis. Remain at bedside and monitor subject until recovery from symptoms.

For Grade 3 or Grade 4 allergic reaction attributed to IV etoposide, it is acceptable to switch to oral etoposide, if clinically appropriate.

5.4.1.8 Ototoxicity

Remove patient from therapy for grade \geq 3 ear and labyrinth disorder (ototoxicity).

5.4.1.9 Grade 3 or 4 Non-Hematologic Toxicity

If patient develops grade 3 or 4 non-hematologic toxicity attributed to protocol therapy but not detailed above [excluding the following: anorexia, fatigue and fever without grade 3 or 4 neutrophil count decrease (neutropenia)] hold all therapy. Therapy can be restarted if the toxicity has resolved to < grade 1 by the time of the next treatment. Doses of all chemotherapy should then be reduced by 25% (of the dose received during the previous cycle). If carboplatin administered, reinstitute carboplatin AUC with decrease by one dose level (i.e. starting dose of AUC 6 dose reduction 1= AUC 5). If chemotherapy is held for more than 3 weeks, remove the patient from all protocol therapy.

A clinically relevant overlap in toxicity may arise between the immune-related dermatologic and cardiac toxicities attributed to nivolumab and dermatologic and cardiac toxicities attributed to etoposide. The management of overlapping toxicities should be guided by clinical judgment and an assessment of the most likely causative etiology, with special consideration given to the potential

for immune-mediated toxicities. Nivolumab administration should be delayed for toxicities as indicated in the management algorithms ([Appendix III](#)) that in the opinion of the treating physician are related to nivolumab. Please refer to Section [5.4.2.2](#).

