5.2.2 Terminology

- **Adverse Event (AE):** Any untoward medical occurrence associated with the use of an agent in humans, whether or not considered agent related. Therefore, an AE can be **ANY** unfavorable and unintended sign (including an abnormal laboratory finding), symptom, or disease temporally associated with the use of a medicinal product, whether or not considered related to the medicinal product.
- **Attribution:** An assessment of the relationship between the adverse event and the protocol treatment, using the following categories.

ATTRIBUTION	DESCRIPTION
Unrelated	The AE is clearly NOT related to treatment.
Unlikely	The AE is doubtfully related to treatment.
Possible	The AE may be related to treatment.
Probable	The AE is likely related to treatment.
Definite	The AE is clearly related to treatment.

- **CAEPR (Comprehensive Adverse Events and Potential Risks List):** An NCI generated list of reported and/or potential AEs associated with an agent currently under an NCI IND. Information contained in the CAEPR is compiled from the Investigator's Brochure, the Package Insert, as well as company safety reports.
- **CTCAE:** The NCI Common Terminology Criteria for Adverse Events provides a descriptive terminology that is to be utilized for AE reporting. A grade (severity) is provided for each AE term.
- **Expectedness:** Expected events are those that have been previously identified as resulting from administration of the agent. An adverse event is considered unexpected, for expedited reporting purposes, when either the type of event or the severity of the event is NOT listed in the protocol or drug package insert.
- **Hospitalization (or prolongation of hospitalization):** For AE reporting purposes, a hospitalization is defined as an inpatient hospital stay equal to or greater than 24 hours.
- **Life Threatening Adverse Event:** Any AE that places the subject at immediate risk of death from the AE as it occurred.

- **Serious Adverse Event (SAE):** Any adverse event occurring at any dose that results in **ANY** of the following outcomes:
 - Death
 - A life-threatening adverse event
 - Inpatient hospitalization or prolongation of existing hospitalization (for ≥ 24 hours).
 - A persistent or significant incapacity or substantial disruption of the ability to conduct normal life functions.
 - A congenital anomaly/birth defect.

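### In Arm A, Section 5.4.1.9 literally applies a permanent chemotherapy cut and a 3-week removal rule to Grade 3-4 events attributed to nivolumab alone, chiefly laboratory abnormalities for which Section 5.4.2.1 needs no stop

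*Combined protocol and SAP*

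**What the plan says.** **Chemotherapy rule.** Section 5.4.1.9 belongs to 5.4.1, whose heading names cisplatin/carboplatin and etoposide. Its trigger is: "If patient develops grade 3 or 4 non-hematologic toxicity attributed to protocol therapy but not detailed above". It exempts anorexia, fatigue, and fever without severe neutropenia, and nothing else. It holds all therapy, allows a restart once the event is below Grade 1 by the next treatment, and cuts every chemotherapy drug by 25% of the previous cycle's dose, or carboplatin by one AUC level. It ends: "If chemotherapy is held for more than 3 weeks, remove the patient from all protocol therapy". The note at the head of 5.4.1 adds: "Dose reductions for all events are permanent and should be for all subsequent cycles".

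A second paragraph of 5.4.1.9 deals with skin and cardiac toxicity that nivolumab and etoposide share: "The management of overlapping toxicities should be guided by clinical judgment and an assessment of the most likely causative etiology". It refers the reader to 5.4.2.2, as does the parallel paragraph on hepatic overlap in 5.4.1.3.

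**Nivolumab rules.** Section 5.4.2 gives nivolumab at full dose, withholds it or stops it. It permits chemotherapy to go on, where suitable, after nivolumab is stopped for its own toxicity. Section 5.4.2.1 sends most Grade 3-4 events off protocol therapy, with exceptions. One exception covers Grade 3-4 laboratory and electrolyte abnormalities that replacement or insulin can control, or that need no treatment: these do not call for discontinuation. Section 5.4.2.2 covers infusion reactions only.

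**The concern.** The trigger of 5.4.1.9 is wider than the drugs it adjusts. A site that follows it to the letter must reduce platinum and etoposide for an event that chemotherapy did not cause, and may have to end all treatment for an abnormality that 5.4.2.1 allows to be managed without stopping. This can happen only in Arm A, and only while chemotherapy is being given. With at most four cycles (Section 5.1), the lost dose is not made up later. What is at stake is treatment of individual patients and consistency between sites.

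**Working it through.** **1. Reach of the trigger.** Sections 5.1 and 5.6 make nivolumab part of Arm A treatment. Section 5.2.2 defines attribution as "An assessment of the relationship between the adverse event and the protocol treatment", that is, against the treatment as a whole. This is a reporting definition, so it supports the reading but does not settle it. Section 5.4.1.1 shows that narrower wording was available: "For treatment delays (hold both chemotherapy and nivolumab) due to chemotherapy toxicities of more than 7 days". The limit to events not already detailed reaches back to 5.4.1.1-5.4.1.8 only, so it does not exclude events handled later in 5.4.2.1.

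**2. The rules side by side, for an event attributed to nivolumab alone in cycles 1-4.**

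| Event | Nivolumab sections | 5.4.1.9, read literally | Result |
|---|---|---|---|
| Grade 3-4 laboratory abnormality, controlled or needing no treatment | No discontinuation required (5.4.2.1) | Hold everything, cut chemotherapy, remove after a chemotherapy hold of more than 3 weeks | Clearest conflict |
| Nivolumab stopped for its own toxicity without an off-protocol-therapy instruction | Chemotherapy may go on if suitable (5.4.2) | Same | Smaller conflict |
| Grade 3 rash | Hold to Grade 1 or less, then may resume (5.4.2.1) | Same, but with causal judgment on skin overlap | Partial |
| Grade 3-4 infusion reaction | Stop nivolumab (5.4.2.2) | Largely covered by 5.4.1.7, or pointed to 5.4.2.2 | Largely resolved |
| Events that 5.4.2.1 takes off protocol therapy | Off | Off or held | Not part of this point |

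In the first row the direct clash is over removal. Section 5.4.2.1 does not require nivolumab to stop, while 5.4.1.9 stops it once chemotherapy has been held more than 3 weeks.

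**3. Detection.** Glucose is in the chemistry panel before each treatment (7.1, footnote 2), and hyperglycemia is a listed nivolumab risk (5.3). Amylase and lipase are required only on day 1 of cycle 1 and when clinically indicated (7.1, footnote 4).

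**4. Dose lost per affected patient.** One cut after cycle k of 4 removes (size of cut) x (4 - k)/4.

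| | k = 1 | k = 2 | k = 3 |
|---|---|---|---|
| Cisplatin or etoposide, 0.25 | 18.75% | 12.5% | 6.25% |
| Carboplatin AUC 6 to 5, 1/6 | 12.5% | 8.3% | 4.2% |
| Carboplatin AUC 5 to 4, 1/5 (assumed; the level below 5 is not stated) | 15% | 10% | 5% |

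For cisplatin, 4 x 75 = 300 mg/m2 becomes 243.75, 262.5 or 281.25 mg/m2. Removal after cycle 1 loses 3 of 4 cycles. That is a worst case, because the documents give no probability of a hold longer than 3 weeks.

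**5. Number of patients.** Arm A has 67 eligible and treated patients (9.4).

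- Lipase: Section 1.3 reports no Grade 3-4 cases on nivolumab 3 mg/kg. The cohort size follows from the reported 13 (13%) and 6 (6%), giving n of about 97 to 104. The one-sided 95% upper bound is 1 - 0.05^(1/n): 3.04% at n = 97 and 2.84% at n = 104. Times 67, this is 2.0 and 1.9 patients.
- Hyperglycemia: Section 5.3 lists it in the category below 3%, so under 0.03 x 67 = 2.0 patients. This is a frequency category, not a Grade 3-4 rate.
- For scale, the partly affected events: Grade 3-4 rash below 1% (1.2.1.4), under 0.67 patients; Grade 3-4 infusion reactions none of 287 (1.2.1.4), upper bound 1.04%, or 0.70 patients.

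These figures do not describe nivolumab plus chemotherapy over four cycles. Section 1.2.1.4 mentions Grade 3-4 rash with nivolumab plus platinum doublets but gives no count.

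**6. Power.** The plan states 88%. Schoenfeld's formula with 113 events and hazard ratio 0.625 gives sqrt(113)/2 x 0.470 - 1.2816 = 1.217, or 88.8%. The dosing rule does not enter this calculation.

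**The case against.** The strongest reply is that the two sections adjust different drugs. The tables in 5.4.2.1 set the next nivolumab dose and are silent on chemotherapy; a hold with a 25% cut is not discontinuation. Under a chemotherapy heading, in rules that 5.4 calls guidelines, a sensible site would use the nivolumab section for a nivolumab-only event. Holding drugs together is deliberate: 5.4.1.3 does so "so that all drugs are kept on the same schedule". Grade 3 hyperglycemia in these cycles is also confounded by dexamethasone premedication (5.1, 5.5) and by the admission of patients with type I diabetes (3.1.16), so attribution to nivolumab alone will be uncommon.

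Much of this stands. It confines the direct clash to removal, lowers the expected count further, and leaves rash only partly affected. It does not supply an exemption. The causal-judgment sentence covers skin and cardiac overlap, not laboratory or endocrine events. The precedence sentence in 5.4.2.1 ranks the protocol over the Appendix III algorithms, not 5.4.2 over 5.4.1.9.

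A reader might infer more, and the documents do not support it:

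- *The 3-week and 12-week limits contradict each other.* They govern different drugs, chemotherapy and nivolumab.
- *Using up one of two permitted reductions is a separate harm.* The limit is "Patients may receive a maximum of two chemotherapy dose reductions", but with four cycles reductions can occur only before cycles 2, 3 and 4. A third could arise only before cycle 4 and would cost at most one cycle.
- *The rule biases or weakens the PFS comparison.* No rate for this setting is given, and patients who stop therapy early are still followed for progression and survival (5.7).

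**Conclusion.** The point holds in a narrow form. Read literally, 5.4.1.9 requires a permanent chemotherapy cut, and possibly removal from all therapy, for Grade 3-4 events attributed to nivolumab alone. The clearest cases are laboratory abnormalities that 5.4.2.1 exempts from discontinuation; a smaller one arises where 5.4.2 lets chemotherapy go on after nivolumab is stopped. Separately, the pointers in 5.4.1.3 and 5.4.1.9 lead to infusion reactions, while the hepatic and skin tables are in 5.4.2.1.

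At most a few of the 67 Arm A patients would be affected. That rests on borrowed rates and on the assumption that sites apply the trigger as written; some would not. The correction is worth making because the instructions differ for the same patient and the repair is simple.

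**What to change.** - In 5.4.1.9, limit the 25% reduction (one AUC level for carboplatin) and the 3-week removal rule to events attributed at least in part to cisplatin, carboplatin or etoposide.
- Add that, in Arm A, events attributed to nivolumab alone follow 5.4.2 and 5.4.2.1 without a chemotherapy dose reduction, and that the treating physician may hold chemotherapy while the event is active.
- In 5.4.1.3 and 5.4.1.9, point to 5.4.2.1, keeping 5.4.2.2 for infusion reactions.
- Leave the off-protocol-therapy rows of 5.4.2.1 as they are.

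The cost is a short amendment with clinical sign-off, because a dosing rule changes, and notice to sites. It needs no new data, patients or procedures, and drugs can still be held together.
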